
The results of the interim analysis will be judged by the DSMB. This committee will act completely independently of the clinical investigators, including the Principal Investigator. However, the ultimate decision to stop the study will rest with the Principal Investigator.

8 Safety and Adverse Events

8.1. Definitions

Adverse Event

An **adverse event** (AE) is any symptom, sign, illness or experience that develops or worsens in severity during the course of the study. Not all events that would traditionally be defined as AEs will be collected by the sponsor for this trial.

There are a number of expected side effects related to the medical management of miscarriage with misoprostol including abdominal cramping, vaginal bleeding, fevers, chills, nausea, vomiting, diarrhea, dizziness, and endometritis. Sepsis (infection of the bloodstream): sepsis is a known risk related to any type of spontaneous or induced abortion. There have been reports of deaths due to sepsis in women who have had induced abortion with mifepristone and misoprostol. Most of these women were infected with the same type of bacteria, known as *Clostridium sordellii*. The symptoms in these cases of infection were not the usual symptoms of sepsis. It is not known whether using mifepristone and misoprostol caused these deaths. Reports of fatal sepsis in women undergoing medical abortion are very rare (approximately 1 in 100,000). There is also the chance that uterine aspiration will be required in the setting of failure or emergency. These symptoms will be collected from patient self-report and subject diaries, but may also be discovered in the medical record. The only non-serious events that will be specifically collected by the sponsor and classified as AEs for this study are those that are both unexpected and considered to be related to study procedures or study drug. All attempts will be made to obtain records of care obtained outside the study sites for adverse events that are possibly related to the study treatment. Subjects will be informed that these records may be needed, and will be asked to sign a release form when they enroll in the study.

All adverse events will be collected, recorded, and assessed locally by the investigator or his/her designee. Events that are determined to be both unexpected and related to the study will be entered into the electronic CRF and thus reported to the sponsor.

Serious Adverse Event

Adverse events are classified as serious or non-serious. A **serious adverse event** is any AE that is:

- fatal
- life-threatening
- requires or prolongs hospital stay
- results in persistent or significant disability or incapacity
- a congenital anomaly or birth defect
- an important medical event

Important medical events are those that may not be immediately life threatening, but are clearly of major clinical significance. They may jeopardize the subject, and may require intervention to prevent one of the other serious outcomes noted above.

All serious adverse events will be reported to the medical monitor, regardless of causality assessment. Serious adverse events will also be reported by the sponsor to the FDA and to Danco Laboratories, Inc.

If a subject becomes pregnant again after resolution of her EPF within the 30 day study window, this will not be considered an adverse event and will not be followed.

Adverse Event Reporting Instructions

Any serious adverse event or concomitant illness, whether or not it is considered related to the study medication, will be reported by telephone, email or fax within 24 hours of awareness to the study sponsor:

[name], MPH
[contact]
[contact]
[contact]
Email: [contact]

The investigator will complete a SAE Form, which will be sent immediately (preferably by fax) to the study sponsor. A SAE form will be completed for any SAE that is experienced after the subject has signed the Informed Consent Form.

The Principal Investigator will submit updated SAE. The Principal Investigator will evaluate women who experience a SAE as necessary until the event is resolved. Adverse events that are both serious and unexpected will be reported to the FDA per the Federal Code of Regulations 21 Part 312.32 (IND Safety Reports).

It is the responsibility of the study sponsor to notify all participating investigators, in a written IND safety report, of any adverse event associated with the use of the drug that is both serious and unexpected, as well as any finding from tests in laboratory animals that suggest a significant risk for human subjects. Additionally, sponsors are also required to identify in IND safety reports all previous reports concerning similar adverse events and to analyze the significance of the current event in light of the previous reports.

The study sponsor will also report all SAEs to the FDA and to Danco Laboratories, Inc.

The principal investigator will report adverse events for review by the IRB/EC per their local reporting requirements.

Adverse Event Reporting Period

The study period during which adverse events must be reported is normally defined as the period from the initiation of any study procedures to the end of the study treatment follow-up. For this study, the study treatment follow-up is defined as 30 days following the last administration of study treatment.

Post-study Adverse Event

All unresolved adverse events should be followed by the investigator until the events are resolved, the subject is lost to follow-up, or the adverse event is otherwise explained. At the last scheduled visit, the investigator should instruct each subject to report any subsequent event(s) that the subject, or the subject's personal physician, believes might reasonably be related to participation in this study. The investigator should notify the study sponsor of any death or adverse event occurring at any time after a subject has discontinued or terminated study participation that may reasonably be related to this study.

The sponsor should also be notified if the investigator should become aware of the development of cancer or of a congenital anomaly in a subsequently conceived offspring of a subject that has participated in this study.

Hospitalization, Prolonged Hospitalization or Surgery

Any adverse event that results in hospitalization or prolonged hospitalization should be documented and reported as a serious adverse event unless specifically instructed otherwise in this protocol. Any condition responsible for surgery should be documented as an adverse event if the condition meets the criteria for an adverse event.

Neither the condition, hospitalization, prolonged hospitalization, nor surgery are reported as an adverse event in the following circumstances:

- Hospitalization or prolonged hospitalization for diagnostic or elective surgical procedures for a preexisting condition. Surgery should **not** be reported as an outcome of an adverse event if the purpose of the surgery was elective or diagnostic and the outcome was uneventful.
- Hospitalization or prolonged hospitalization required to allow efficacy measurement for the study.
- Hospitalization or prolonged hospitalization for therapy of the target disease of the study, unless it is a worsening or increase in frequency of hospital admissions as judged by the clinical investigator.

9 Recording of Adverse Events

At each contact with the subject, the investigator must seek information on adverse events by specific questioning and, as appropriate, by examination. Information on all adverse events should be recorded immediately in the study documents.

All adverse events occurring during the study period must be recorded. The clinical course of each event should be followed until resolution, stabilization, or until it has been determined that the study treatment or participation is not the cause. Serious adverse events that are still ongoing at the end of the study period must be followed up to determine the final outcome. Any serious adverse event that occurs after the study period and is considered to be possibly related to the study treatment or study participation should be recorded and reported immediately.

10 Data and Safety Monitoring Plan

Patient safety will be monitored continuously by the Sponsor-Investigator, [name]. [name] will serve as the medical monitor for the study. The Principal Investigator at each site has the primary responsibility for identifying potential adverse events experienced by study participants and reporting the experience as outlined in the protocol to the Sponsor and to the IRB as required by local standards. The Sponsor-Investigator is responsible for reviewing these reports and making the final determination of relatedness, reporting to the medical monitor, and distributing reports to the other site investigator as needed.

Data Monitoring

Monitor Selection and Training

One monitor will be assigned for this trial and will be responsible to complete the monitoring process. The monitor will be an employee of the University of Pennsylvania Women's Health Research Center

who is not involved in the local site conduct of the study. The monitor will have experience in the conduct of clinical research and will be familiar with research regulations and Good Clinical Practice. The monitor will be trained by the University of Pennsylvania Office of Clinical Research and supervised by the Sponsor-Investigator. Training will include review of 21 CFR 312, ICH GCP, safety and adverse event review and reporting, the study protocol, the study database, the informed consent forms and processes from each site, and this monitoring plan.

Study Initiation

A Study Initiation Visit will be conducted with each participating site PI and key study personnel.

The Principal Investigator at each site will ensure that he or she understands and accepts responsibility for the protocol and the requirements for an adequate and well-controlled study; the obligation to conduct the clinical investigation in accordance with the applicable federal regulations; the obligation to obtain informed consent in accordance with 21 CFR Part 50; the obligation to obtain IRB review and approval of a clinical investigation before the investigation may be initiated and to ensure continuing review of the study by the IRB in accordance with 21 CFR Part 56; and to keep the sponsor informed of such IRB approval and subsequent IRB actions concerning the study.

Monitoring Activities

Frequency

Enrollment will be complete when 300 subjects are enrolled into the trial. Approximately 6 subjects will be enrolled per month across both sites. Monitoring will be conducted periodically throughout the study as described below:

- The **first monitoring time-point** will occur after the first 5 subjects have been enrolled at the site and have reached clinical resolution, OR after 12 months have passed since study initiation, whichever occurs first.
- If no issues of concern are noted during the first monitoring time-point, subsequent monitoring will occur at least annually.
- The **final monitoring time-point** will be conducted when 100% of the subjects have been enrolled and completed the study. This visit will also serve as the close-out monitoring visit

Additional monitoring may occur on an as-needed basis as determined by the Sponsor.

Data Review

All database entries for the first 5 subjects at each site will be 100% source data verified. In addition, the database entries for one in every cohort of 10 subjects at each site will be 100% source data verified.

If a greater than 10% error rate is noted during the data review, the monitor will request additional documents to source verify 100% of the data on a larger sample.

The following variables will be 100% source data verified for *all* subjects enrolled in the study.

- Informed Consent
- Inclusion/Exclusion Criteria
- Drug Accountability
- Serious Adverse Events
- Primary Outcomes/Endpoint Data Verification

Regulatory Document Review

The Regulatory Documents will be maintained at each site in the Regulatory Binder, with all applicable documents additionally maintained by the Sponsor. The Regulatory Binder will be reviewed by the monitor in an ongoing manner.

Documentation of Monitoring Activities

Monitoring Log

The monitor is required to sign and date the monitoring log documenting the dates of the monitoring activity.

Monitoring Report

All monitoring activities will be documented on the Monitor's Report and Visit Checklist. The original report for each visit will be filed in the Sponsor section of the Regulatory Binder.

Data Management

Most of the data will be directly entered into REDCap – the source itself therefore is a secure, web-based database. Any other data will be entered directly from source documents into REDCap, a secured, web-based study database that complies with Title 21 CFR Part 11. This database will be maintained at the University of Pennsylvania. Data will be entered by site personnel delegated by the site Principal Investigator to perform this function. Double data entry will not be used. Data queries and database corrections will be performed by staff at the University of Pennsylvania responsible for maintaining the database.

Study Close Out

The monitor will conduct the study close out at the time of the final monitoring time-point and within 3 months after the last patient has completed the study.

The following activities will be completed by the monitor to close out the study:

- Ensure all data has been reviewed and collected;
- Ensure all outstanding queries are answered;
- Confirm all Serious Adverse Events, if applicable, have been reported to the IRB(s) and the FDA;
- Review the Regulatory documentation and Subject Files for completeness and compliance with GCP and all applicable federal regulations;
- Ensure all protocol violations were submitted to the IRB per local requirements;
- Ensure that all continuing review reports were submitted to the IRB;
- Perform drug accountability; and
- Review requirements for record retention with the investigator and the clinical staff.

11 References

1. Casterline JB (1989) Collecting data on pregnancy loss: a review of evidence from the World Fertility Survey. *Stud Fam Plann* 20: 81-95.
2. Jones RK, Kost K (2007) Underreporting of induced and spontaneous abortion in the United States: an analysis of the 2002 National Survey of Family Growth. *Stud Fam Plann* 38: 187-197.
3. Jurkovic D (1998) Modern management of miscarriage: is there a place for non-surgical treatment? *Ultrasound Obstet Gynecol* 11: 161-163.

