7.2. Statistical Methods

Primary Analysis: Baseline demographic characteristics of the subjects in the two groups will be examined. If the randomization is executed correctly, we expect no significant difference between the two groups on these variables. If there is an imbalance on certain variables (mostly likely by chance) and these variables also affect the outcomes variables, we will control for these variables using indirect standardization, Mantel-Haenzel stratified analysis or multivariable logistic (for categorical outcome) or linear regression (for continuous outcome). If there is a gross imbalance between the two groups, we will conduct in-depth evaluation to identify factors that may adversely affect randomization. Multivariable logistic and linear regressions will be used to adjust for the imbalance.

We will explore outcomes by clinical site; if there is no significant overall difference among the sites (homogeneous), we will pool sites together. However, if there is significant overall difference, we will identify which site(s) differ from others. Pairwise comparison will be conducted with Scheffe adjustment of significance level. In all following analyses, site will then be an independent variable for adjustment.

Both intent to treat and compliant populations will be analyzed. For categorical data, chi-square test will be used. For continuous variables, t-test will be used if the distribution is normal; otherwise rank-sum test or log transformation will be used. The following outcomes will be evaluated:

- Success rates between study arms for early pregnancy failure;
- Frequency of side effects and serious adverse events between study arms;
- Patient's satisfaction, anxiety, and acceptability of the treatment regimens;
- Cost analysis to compare these two treatments.

The outcome is defined as gestational sac expulsion with one treatment dose on Study Day 3 and no need for surgical intervention or medical intervention within 30 days of treatment. The overall success proportion, along with 95% confidence intervals, will be calculated for each treatment group. The

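### The target-disease exemption in section 8.1 is broad enough to leave unplanned admissions for bleeding or aspiration after study drug out of the serious adverse event count

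*Combined protocol and SAP*

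**What the plan says.** Section 8.1, under the subheading on hospitalization and surgery, starts from a general rule: "Any adverse event that results in hospitalization or prolonged hospitalization should be documented and reported as a serious adverse event unless specifically instructed otherwise" in the protocol. It then gives such an instruction: "Neither the condition, hospitalization, prolonged hospitalization, nor surgery are reported as an adverse event in the following circumstances". Three circumstances follow. The third is "Hospitalization or prolonged hospitalization for therapy of the target disease of the study, unless it is a worsening or increase in frequency" of admissions; the exception in full reads "unless it is a worsening or increase in frequency of hospital admissions as judged by the clinical investigator". Neither the target disease nor worsening is defined for this purpose.

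Elsewhere in 8.1, an adverse event that requires or prolongs a hospital stay is serious, and the reporting instruction is wide: "Any serious adverse event or concomitant illness, whether or not it is considered related to the study medication, will be reported" within 24 hours. The same section lists vaginal bleeding among the expected side effects of medical management and adds: "There is also the chance that uterine aspiration will be required in the setting of failure or emergency".

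Section 7.2 lists as an outcome "Frequency of side effects and serious adverse events between study arms". Section 7.4, item 4(b), brings SAEs adjudicated as potentially related into the interim safety look.

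**The concern.** The exemption fits a chronic illness with recurrent admissions, where a routine admission for the disease says little about the study drug. Here the disease is a single episode, the study drug is its treatment, and the main alternative treatment is aspiration. An admission to complete the miscarriage after study drug may be ordinary treatment of the disease or a harm of the regimen, and the wording does not separate the two.

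If sites apply the exemption broadly, admissions that a reader would expect in the SAE table will not be there. Serious events are likely to be few, so a handful of omissions matters. The judgement that can restore reporting lies with someone who probably knows the arm.

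**Working it through.** The plan states no figure on this point. The check is to follow one event through the text: a woman admitted for aspiration while bleeding after misoprostol.

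1. **General rule.** An adverse event leading to hospitalization is an SAE unless the protocol instructs otherwise (8.1).
2. **Carve-out.** The list of circumstances is that contrary instruction. Its lead-in covers the condition, the admission and the surgery together.
3. **Does the event fit?** The target disease is early pregnancy failure (section 2). Treatment means emptying the uterus (1.1), and aspiration is one of the options for a persistent sac (6.3, 6.4). The admission can be read as treatment of the target disease.
4. **Does the exception rescue it?** If worsening stands alone, haemorrhage could qualify. If both nouns attach to hospital admissions, the phrase has little meaning for a single admission in a 30-day window. The text does not choose, and it gives the investigator no criteria.
5. **Consequence if exempt.** In 8.1 an SAE is a kind of adverse event. What is not reported as an adverse event cannot be an SAE, so the 24-hour rule is not triggered.
6. **Backstop.** The only non-serious events collected by the sponsor are those both unexpected and related (8.1). Bleeding is listed as expected. Section 9 requires adverse events to be recorded in the study documents, but that does not place them in the SAE comparison. Full source verification of SAEs (section 10) would not flag an omission that follows 8.1.
7. **Who judges?** Group 2 alone swallows mifepristone at the visit (6.2), no placebo is described, and only the ultrasonographer is called masked (6.3, 6.4). That the investigator knows the arm is an inference, but a fair one.
8. **Equal between arms?** The rule is the same in both arms, but the number of women exposed to it need not be. With the planning success rates of 70% and 85% (7.1) and 150 per arm, expected failures are 150 × 0.30 = 45 on misoprostol alone and 150 × 0.15 = 22.5 on the combination. These are women who may need further treatment, not admissions.

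**Scale, on assumed rates only.** If 1–3% of women per arm are admitted for bleeding or aspiration, that is 150 × 0.01 = 1.5 to 150 × 0.03 = 4.5 per arm, or 3 to 9 in the trial.

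To show how sensitive small counts are, borrow the 2% and 6% that section 7.4 uses for infection, with n = 150 per arm and two-sided α = 0.05:

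power = Φ{(|p₂ − p₁|√n − 1.96√(2p̄(1 − p̄))) / √(p₁(1 − p₁) + p₂(1 − p₂))}

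With p₁ = 0.02, p₂ = 0.06 and p̄ = 0.04, this is Φ{(0.490 − 0.543)/0.276} = Φ(−0.19) ≈ 42%, on 3 versus 9 expected events.

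| Share unreported | Power, both arms affected | Combined arm only: observed rate | Power |
|---|---|---|---|
| 25% | 33% | 4.5% | 23% |
| 50% | 23% | 3.0% | 8% |
| 75% | 14% | 1.5% | 5% |

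In the last row the combined arm's observed rate falls below the control's 2%. The documents support none of these shares. The table shows sensitivity and does not forecast.

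**The case against.** The strongest reply is that 8.1 is a general rule with ordinary carve-outs, and that haemorrhage after study drug is not the disease. Bleeding is listed as a side effect of treatment, an admission for it meets the hospital-stay criterion, and in a woman enrolled as haemodynamically stable it could well be called a worsening. Life-threatening and important medical events are serious in their own right. This stands as far as it goes: the text is ambiguous on haemorrhage. It does not show that the exemption is safe, because two sites could classify the same admission differently and both comply.

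A reader might infer more than the documents support:

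- **That exemption is at the investigator's discretion.** It applies by default. Judgement only restores reporting.
- **That any emergency aspiration is exempt.** The third circumstance names hospitalization. Surgery enters through the lead-in and only within that circumstance, so an outpatient aspiration is not exempted by it. The same subheading has a condition leading to surgery documented if it meets the adverse event criteria.
- **That 8.1 flatly contradicts itself.** The general rule expressly allows exceptions. The fault is the breadth of one exception.
- **That the events vanish from the trial.** Surgical or medical intervention within 30 days is a primary-outcome failure (7.2), and primary endpoint data are fully source-verified (section 10). The day-30 call records further treatment (6.5), and costs include emergency visits (7.2). What can be lost is the place in the SAE count. The failure count does not replace it, because it does not separate a planned aspiration from an emergency admission.
- **That interim stopping would be distorted.** The numerical limits in 7.4 item 4 concern failure and infection. Other SAEs enter only if adjudicated as potentially related.
- **That most SAEs would be lost, or that one arm is favoured.** The documents give neither an admission rate nor an exempted share, and sections 1.2 and 1.3 describe complications as rare or low.

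**Conclusion.** The point holds as one about scope. By default, the third exemption takes admissions for treatment of early pregnancy failure out of adverse event reporting, and so out of the SAE count. It is worded broadly enough to include unplanned admissions for bleeding or aspiration after study drug. That could under-count SAEs in the 7.2 comparison and in the interim review of related SAEs in 7.4.

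The size is unknown. On the assumed 1–3%, the admissions at issue number 1.5 to 4.5 per arm. Moving two or three could change the direction of the observed difference, but that would not amount to a significant finding either way. The conclusion rests on two readings: that uterine evacuation is treatment of the target disease, and that the clinical investigator knows the arm. It does not extend to outpatient aspirations or to the primary outcome.

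**What to change.** Reconcile the adverse event definitions, reporting and recording rules in sections 8.1 and 9 as follows:

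- Limit the third exemption to admissions for planned aspiration chosen under 6.3 or 6.4 without an acute complication.
- State that any unplanned hospital admission after study drug is reported as an SAE in both arms.
- Remove the limb of the exception on frequency of admissions and the reference to the investigator's judgement. If worsening is kept, define it.
- In the 7.2 analysis, tabulate all post-treatment admissions by arm, whatever their reporting status. This table does not depend on how a site classifies an admission as planned or unplanned.

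Outpatient emergency aspirations should stay under the existing seriousness criteria in 8.1. Making each one an SAE would go beyond what is needed.

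The cost is a one-sentence amendment, one table and a few more SAE forms. Patient care does not change.
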